## 11. Procedures Involved\*

## Focus groups (Part 1)

Focus groups will be used to help inform the app development and will include patients, patient caregivers, and provider participants. Focus groups with patients and patient caregivers will occur together, and provider focus groups will be conducted separately. Focus groups will last for approximately 60 minutes. Qualitative data analysis will generate aggregated preferences and recommendations about smartphone application message components, user interface, reporting, alerts, and watch functions. Focus group/interview analyses will inform the Hack-a-thon and finalize the Pulsewatch design.

All participants (patients, caregivers, and providers) will be told by the study team that their feedback is appreciated and if they feel uncomfortable at any time of the focus group, they have the right to refuse to answer any question(s) and the right to opt-out of the study at any time.

**Part I:** Semi-structured and open-ended agendas for the focus groups and/or provider interviews have been written and are submitted as part of our application packet. Discussions will be audio-recorded and transcribed, protecting confidentiality by replacing participants' names with study IDs. Focus groups will begin with a broad description of the Pulsewatch system (including smartphone app and watch), its purpose, and general functionality. Each participant will be given a smartwatch and smartphone programmed with the Pulsewatch app and AliveCor ECG app and will be asked to use them during the focus group. In keeping with contemporary user-centric app design processes, facilitators will interact with participants as they use the smartwatch and smartphone app. After users have time to wear the watch, perform an ECG, review their data, and use the annotator, we will invite them to ask open-ended questions to explore elements such as the following: the layout of the result and summary screens, including the graphical representation of heart rate and rhythm (e.g., bar graph, slider, stoplight, faces); alert and adherence prompts, including the number of acceptable prompts that Pulsewatch can deliver per day; opinions about personalized intervention messages (e.g., "[name], you've not checked your ECG"); and their preferred timing.

Provider interviews will also explore what data outputs the clinicians consider ideal, along with when and how often they would want to receive them. We will conduct up to 6 focus groups with participants and up to 2 focus groups with providers as part of Part I over a 6-month period, then will pause to review the data. If there is strong consensus or saturation on key areas, we will stop.

## Hack-a-thon (Part 1):

Pulsewatch ISP V 1.5 Docket#: H00016067

#### PULSEWATCH INVESTIGATOR STUDY PLAN

The PI, Co-Is, 4 participants, 4 provider champions, and computer programmers and engineers from the University of Connecticut (UConn) will meet at the University of Massachusetts Medical School (UMMS) in a conference room to create the final Pulsewatch technology to be deployed in Aims 2 and 3. Modeled on "Hack-a-thons" in the software engineering industry, we will drive innovation by creating team synergy and accelerating product development. This meeting will likely occur in the Albert Sherman Center 7th floor conference room. Patient participants will receive parking vouchers and compensation. Providers will not be compensated. Light refreshments will be provided for all. The meeting will take place over a single day (8-hours) to accommodate the busy schedules of providers and participants. After the Hack-a-thon, the study team will meet to review and encode changes to the application.

The purpose of the Hack-a-thon meeting is to optimize the interactivity and usability of Pulsewatch, guided by information gleaned from focus groups. Using this format, end users (providers and patients) can suggest changes, and programmers will make modifications in realtime. Using a combination of focus groups and agile programming is an innovative as well as sound approach to designing apps. This event will be a critical aspect for Aims 2 and 3 to help develop the interface and management of the app for patients to use. At the Hack-a-thon, participants will be asked to use a prototype of the Pulsewatch app and the system, and then provide feedback on what they think of the system. Programmers will make modifications to the application in real time. While programmers are making those modifications, participants may take a break during the Hack-a-thon, and then come back at a later time during the event to see the final product.

The individuals who will be invited to this Hack-a-thon event will be participants and providers from the focus groups. At the focus groups, we will provide a fact sheet about the day-long Hack-a-thon and a contact sheet for people who may be interested in being invited. We will explain that they may accept or decline the invitation. (Please see Fact Sheet: Patient Hack-a-thon in our eIRB submission). Study staff will follow-up with interested participants and providers by telephone or email. Participants will have the option to opt-out or confirm their attendance at the Hack-a-thon.

**Part II, Trial Phase-** The trial phase of the study will occur after the design and development of the Pulsewatch system (app and watch algorithms) is complete (Part I). For Aim 2 of Part II, participants will be randomized into either the intervention or control arm of the study. The Aim 2 control participants will wear a gold standard cardiac monitor patch (two patches over the 14-days) but will not be offered use of the Pulsewatch system. Please view visual Diagram 1a for an overview of the 14-day participant process.

[figure not shown]

Diagram 1a. Participant process of trial phase: Group names are corresponding to the Part II Consent V1.2 form submitted in eIRB.

## Part II:

At baseline, participants in the Aim 2 control group (up to n=30) will be given two gold-standard Cardiac Insight Cardea Solo patch monitors. Each patch will run for 7-days to automatically monitor for and capture irregular heartbeat data. This patch goes right over a participant's heart on their skin. This patch will allow participants to go home with a continuous AF monitoring method without the hassle of carrying around a bulky Holter device. Our PI has already worked with similar devices in the past and has built a relationship with the study team to ensure proper care and transmission of the data. Trained study staff will place the patch on the participant at

[figure not shown]
the baseline visit. There is little risk to the participant from this device, which is widely used technology. The major risk with this device is participant discomfort or skin irritation. Participants will be given a number to contact in the event they have discomfort in the 14 days of using the device. Participants will be given a handout with instructions and care tips for the patch (see Device Handout in eIRB). Only certain sections of this handout will be given to participants depending on which arm of the trial they are assigned to. Aim 2 control participants will be asked to remove the first patch at the end of day 7 and replace it with the second provided patch and wear it for the next 7 days. They will be asked to return both patches at their follow-up visit (approximately 14 days). At their study visit, the participants will be asked to complete an exam and questionnaire that includes standardized scales. Aim 2 control participants will be compensated for their time and effort, as outlined above. The device will be read by a study physician blinded to intervention/control status. Abnormal findings on the monitoring patch, in either the intervention or control groups, will result in notification to the participant's treating physician.

All participants will be given a Device Handout regarding instruction for the appropriate devices they are given. In addition, the study team will review with each participant all instructions regarding how the Cardiac Insight patch functions and the participant's responsibility. The participant will also go home with information regarding the patches (see in eIRB, Cardea Solo Quick start guide- this will be added the Device handout). The study team, specifically the PI, may need to contact participants directly about their results. This will be disclosed in the informed consent form that participants sign.

The Aim 2 intervention participants (up to n=90) will be asked to use the same gold-standard Cardiac Insight patch monitor device for 14 days as the control group described above. Aim 2 intervention participants will also be given a Samsung smartwatch and a Galaxy smartphone. The Samsung smartwatch and Galaxy smartphone are standard devices that are sold commercially and will be labeled, nonetheless, as research devices. If the participant has a smartphone that is compatible to our Pulsewatch app, then we will download the app onto the participant's smartphone.

The Aim 2 intervention group (up to n=90) will be asked to self-monitor using the Pulsewatch system for at least 9 hours daily for 14 days. The intervention system is designed to be minimally intrusive. Participants will be asked to return all study devices (2 Cardiac Insight patches, Samsung smartwatch, and Galaxy smartphone) at the end of their 14 days of use at the follow-up study visit. Participants will be asked to complete a questionnaire at this follow-up study visit and will be compensated.

At enrollment in Part II, all study participants will be informed of the possibility that they may be randomly selected at the completion of their 14-day monitoring period to use the Pulsewatch system for up to 30 days. We chose to assign a larger proportion of participants to the Aim 2 intervention group because the primary analyses for Aims 2 and 3 are focused on Pulsewatch users.

**Diagram 1b. Participant process of Part II, trial phase. This diagram outlines what the participant process is after 14 days and after 44 days. Group names are corresponding to the Part II Consent V1.2 form submitted in eIRB.** Please note: for this "Randomization\*" we would like to ask permission from the IRB for an adaptive plan; refer to section 13 Data Analysis and Management, sub section AF Detection Analysis for this plan. We have provided further details about this process below.

To accomplish Aim 2, we will examine the performance of Pulsewatch monitoring compared to conventional cardiac monitoring for pAF detection (accuracy of detection). We will also explore the participant factors (e.g., hearing or cognitive impairment) associated with app performance.

By enrolling patients from both inpatient and outpatient clinical settings, we will be able to recruit patients who have stroke/TIA and/or who are at risk for stroke (deemed to have a

CHA2DS2-VASc score  $\geq$ 3). At the end at 14 days, if less than 5% of participants have AF based on the gold-standard Cardiac Insight patch, then we would like to ask participants to extend the use of their monitors for further monitoring. (See Section 13, Data Analysis and Management, AF Detection Analysis.)

To accomplish Aim 3, we will randomly select 60 participants from both the intervention group and the control group of Aim 2 at the end of the 14 days and ask them to continue using, or begin using, the Pulsewatch system to upload their pulse recordings. We will also provide participants randomized to the Aim 3 intervention group with a gold standard AliveCor Kardia mobile ECG device to use if they wish to verify their pulse reading from the smartwatch. We will also examine factors (e.g., vision) participants report related to their adherence to using the Pulsewatch system. The 60 participants randomly selected to the Aim 3 control group will not use any devices during this time.

**Part II Exit interviews:** We will use exit interviews for Part II Aim 2 intervention trial participants to identify 'what worked' and 'what didn't work'. The exit interviews will be in addition to the questionnaire and will take place at the same study visit depending on the participants schedule. We will also solicit feedback on the Interactivity Manager and Annotation Panels, features that will be developed too late in Aim 1 to be fully explored by Aim 1 focus groups. We will invite up to 30 Aim 2 intervention participants to complete an exit interview. Exit interviews will happen after the participant's 14-day study visit. These exit interviews will be important for usability data collection and overall feedback from the participants. Each exit interview will last for approximately 30 minutes. Semi-structured tentative and open-ended agendas have been written and submitted to the IRB as part of our packet (see in eIRB, Exit Interview Usability Script V1.0). Discussions will be audio-recorded and transcribed, protecting confidentiality by replacing participants' names with study IDs. Consent for interviews and taping will be part of the study consent.

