## Part II (Aims 2-3):

-To evaluate the performance of a smartwatch for pAF detection in stroke patients and/or to monitor patient who are at stroke risk with  $CHA_2DS_2$ -VASc score  $\geq 3$  by examining over 14 days the accuracy of pAF detection from Pulsewatch vs. a state-of-the-art cardiac monitoring device.

-To evaluate rates of adherence and factors associated with successful longer-term smartwatch use among up to 60 randomly selected stroke patients and/or who have a  $CHA_2DS_2$ -VASc score  $\geq$ 3 enrolled in our 14-day validation study. These randomly selected participants will be asked to use the smartwatch/phone dyad for 30 days. We will explore the impact of smartwatch use over 30 days on patient-reported quality of life, anxiety, and self-efficacy compared up to 60 usual-care patients.

Learnings from these new objectives will support our future goal to extend monitoring periods to many months or years, surpassing the capabilities of event monitors.

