## Adherence Analysis:

In Aim 3 of Part II of the study, adherence will be operationalized to determine whether pulse recordings were present on each day over the 30-day period. We will examine whether participant characteristics, e.g., sex, cognitive impairment, or stroke-related quality of life, affect the likelihood of adherence over the 1-month study period. We will use a mixed effects logistic regression model, including the participant as the random effect to capture the correlation among repeated measures from the same participant, using participant characteristics as the fixed effects, and a binary indicator of daily adherence as the dependent variable. We will also examine the adherence time-trend by including time (day) as a fixed effect in the model and participant as a random effect to estimate the slope of adherence over time. To examine whether the time trend varies by participant characteristics, we will include the interaction between characteristics and time in the model so that the slope of adherence over time can be estimated for each category of participant characteristic variables and be compared among the categories (e.g., pAF diagnosed vs. no pAF). Secondary analyses will examine rates of adherence to Pulsewatch ECG prompts and will compare Pulsewatch users to the usual care group with respect to stroke-related quality of life, anxiety, and self-activation. We will calculate the change score between baseline and 1 month as a dependent variable. First, a t-test will be used to compare 2 study groups on the change score. We will use a linear regression model, which will include group indicator (Pulsewatch users vs. usual care) as the independent variable and possible confounders (e.g., medication adherence and participant demographics) as covariates, to estimate adjusted group differences on the change scores.

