The consent will include permission for follow-up contacts and medical record review, and will also request access to identified proxies, who would be able to help us contact patients in the event they change practices and do not follow up at UMMMC. We will offer modest incentives for recruitment and retention in Pulsewatch: T-shirts and/or bags and/or pens with Pulsewatch logos offered at recruitment and mailed during follow-up.

All participants will be brought back for a study visit approximately 14 days after enrollment. This visit will take place in a research area that is private and comfortable. There, participants will

return both of their patch monitors, smartwatch, and smartphone, and will complete a questionnaire. From the 120 participants in both the Aim 2 intervention and control groups, we will randomly select up to 60 participants to be offered an opportunity to self-monitor at home using the Pulsewatch smartwatch/smartphone for 30 days, as well as the AliveCor ECG recording device. The 60 participants who are randomized into the control arm of Aim 3 will not be offered the opportunity to self-monitor with any device. At the completion of the 30 days, participants in Aim 3's intervention group can either return for a follow-up visit to return all equipment and complete the 44-day follow-up questionnaire, or can return their devices through a prepaid package and complete the 44-day follow-up questionnaire over the phone. Participants in Aim 3's control group will have a choice to complete their 44-day follow-up questionnaire over the phone. Farticipants in Part II of the study will be sent a Fact Sheet reviewing all the details of the process (Fact Sheet: Part II Exit Interviews in eIRB submission). Upon receipt of the study equipment and/or the 44-day questionnaire, the study team will compensate the participants.

Compensation will be given as an incentive. All patients and caregivers who participate will be compensated for their time and efforts in the study as shown in the table below. Providers will not be compensated for participating.

Participant Sub-groups	Compensation	Time Earned					
	Amount						
Part I: Focus Group	\$60.00 gift card	After completing the focus group					
Care-givers	\$60.00 gift card	After completing the focus group					
Part I: Hack-a-thon	\$15/hour gift card	After completing the Hack-a-thon event					
Aim 2: Control group	\$100.00 gift card	After completing the baseline interview					

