## 25. LOCAL NUMBER OF SUBJECTS

There will be a total of up to 170 participants in this study.

Part I: Up to 40 out-patient stroke participants or caregivers and 10 providers. Part II: Up to 120 participants, including 30 in the Aim 2 control group and 90 in the Aim 2 intervention group. Of the 120 participants in both the Aim 2 intervention and control groups, 60 will be invited to participate in the intervention arm of Aim 3 and use the devices for 30 days. At the 14-day follow-up visit, the other 60 participants randomized into the control arm of Aim 3 will be invited to complete a questionnaire in person or over the phone at the end of 30 days.

In order to obtain 170 participants who complete the research, we may over enroll or replace participants who drop out.

Adaptive enrollment design (Part 2): If we struggle to identify sufficient numbers of eligible participants from the inpatient stroke service or clinics over the first 6 months of enrollment (<50% targeted enrollment), we will employ an adaptive design and approach patients presenting to UMMMC out-patient and in-patient cardiology and/or neurology clinics who have high risk for atrial fibrillation and stroke on the basis of a CHADSVASC score >=2. Furthermore, If we struggle to enroll a sufficient number of participants from the UMMS University campus, we will recruit at the stroke treatment centers at UMass Memorial - Health Alliance Hospital in Leominster, MA, and at UMass Memorial - Marlborough Hospital in Marlborough, MA. The PI has actively sought approval from these sites to approach patients from these locations in order to meet study enrollment goals.

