Aim 2 Power: Preliminary data suggest that Pulsewatch will have sensitivity, specificity and AUC of at least .9 to detect pAF. We calculate the width of 95% CI for AUC that ranges from .90 to .95 using the proposed sample size of 90 and an estimated rate of 20% patients with pAF. The width of the 95% CI ranges from .14 to .20. The proposed sample size will therefore give a quite precise estimate of Pulsewatch performance relative to the gold standard.

Aim 3 Analysis: The primary analysis focuses on app adherence use in 30 users asked to continue to use the watch and upload readings daily for 1 month. We will determine daily adherence (yes vs. no) based on whether or not daily smartwatch pulse recordings are present. We will examine whether participant characteristics, e.g., sex, cognitive impairment, or a high degree of stroke-related disability (Barthel Index), affect the likelihood of adherence over the 1 month study period. We will use a mixed effects logistic regression model including the participant as the random effect to capture the correlation among repeated measures from the same participant, uses participant characteristics as the fixed effects, and a binary indicator of daily adherence as the dependent variable. We will also examine the adherence time-trend by

including time (day) as a fixed effect in the model and patient as a random effect to estimate the slope of adherence over time. To examine whether the time trend varies by participant characteristics, we will include the interaction between characteristics and time in the model so that the slope of adherence over time can be estimated for each category of patient characteristic variables and be compared among the categories (e.g., pAF diagnosed vs. no pAF). Secondary analyses will examine rates of adherence to Pulsewatch ECG prompts and will compare Pulsewatch users to the usual care group with respect to stroke-related quality of life, anxiety, and self-activation. We will calculate the change score between baseline and 1 month as dependent variable. First, a *t*-test will be used to compare 2 study groups on the change score. A linear regression model, which will include group indicator (Pulsewatch users vs. usual care) as the independent variable and possible confounders (e.g., medication adherence and patient demographics) as covariates, to estimate adjusted group differences on the change scores.

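### Aim 3 pools both Aim 2 arms, so its usual-care group is mostly former Pulsewatch users, and the Aim 3 models do not name the Aim 2 arm

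*Protocol*

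**What the plan says.** **Source of the Aim 3 sample.** Protocol section 25 plans for Part II "Up to 120 participants, including 30 in the Aim 2 control group and 90 in the Aim 2 intervention group". Under section 11 (Part II), the Aim 2 intervention group "will be asked to self-monitor using the Pulsewatch system for at least 9 hours daily for 14 days". For Aim 3, section 11 says "we will randomly select 60 participants from both the intervention group and the control group of Aim 2" and that staff will "ask them to continue using, or begin using, the Pulsewatch system". Section 24 repeats this: "From the 120 participants in both the Aim 2 intervention and control groups, we will randomly select up to 60 participants". The remaining 60 use no device. The COVID-19 procedures in section 11 spell out both crossing paths: an Aim 2 control who becomes an Aim 3 user is sent the Pulsewatch system, and participants assigned to Aim 3 control send their Pulsewatch devices back.

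**Label.** The objectives (section 4, Part II) speak of 30 days of smartwatch use "compared up to 60 usual-care patients". Section 13 (Adherence Analysis) and the SAP (Aim 3 Analysis) also call the comparator usual care.

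**Models.** The regression for patient-reported outcomes in section 13 has the "group indicator (Pulsewatch users vs. usual care) as the independent variable", with confounders given only as examples. The adherence model is a mixed logistic regression on participant characteristics and day. Neither names the Aim 2 arm. The SAP describes the users as "30 users asked to continue to use the watch and upload readings daily for 1 month", which does not mention new starters.

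**Change score.** Section 11 (Questionnaire) compares change from day 14 to day 44. Section 13 and the SAP (Table 2 and Aim 3 Analysis) use baseline to 1 month.

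**The concern.** A reader of the objectives would expect Aim 3 to compare people given the watch with people who were not. Most of the planned controls, however, will have been asked to wear it for the preceding 14 days. If two weeks of use changes anxiety, quality of life or activation, and some of that change lasts, the controls carry part of the effect and the Aim 3 contrast shrinks. A null result could then mean no effect or a lasting one.

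The primary Aim 3 analysis, adherence over 30 days, has a related difficulty. Continuers and new starters are at different points in their experience of the watch on the same study day, and one slope is fitted through both. The Aim 2 arm is randomised and already on file, so leaving it out of the models gives up interpretability and saves nothing.

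**Working it through.** **1. The plan's own figure.** The SAP (Aim 3 Power) gives 30 vs 30, 80% power, 5% type I error and a detectable effect size of 0.74. Sidedness is not stated; I assume two-sided. The noncentral t gives a detectable d of 0.736, and power 0.805 at d = 0.74. The figure reproduces. At the protocol's 60 vs 60 the detectable d is 0.52. Neither figure depends on who the controls are.

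**2. Make-up of the Aim 3 arms.** Share with prior Pulsewatch assignment = 90/120 = 0.75. Expected number per arm of 60 = 60 × 0.75 = 45, leaving 15 never-users. Under simple random selection (hypergeometric):

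SD = √[60 × 0.75 × 0.25 × (120 − 60)/(120 − 1)] = 2.38; central 95% range 40 to 50 prior users, or 10 to 20 never-users.

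A draw stratified by Aim 2 arm would give exactly 45 and 15. Dropout before day 14, which the documents do not quantify, could shift these numbers.

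**3. Size of any dilution.** Assumptions: watch use shifts a score by d; continuers and new starters end at the same level, so further wear and AliveCor add nothing; a fraction c of the shift persists after the watch is returned.

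Contrast = d − 0.75·c·d = d(1 − 0.75c).

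The expectation is the same measured from day 14: users change by 0.25d, controls by −0.75(1 − c)d, and the difference is again d(1 − 0.75c). With the SAP's d = 0.74, at 60 vs 60:

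| c | Contrast | Power |
|---|---|---|
| 0 | 0.74 | 98% |
| 0.25 | 0.60 | 90% |
| 0.5 | 0.46 | 71% |
| 0.75 | 0.32 | 42% |
| 1 | 0.19 | 17% |

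No value of c is given in the documents, so this is a range and not a forecast.

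**4. Chance imbalance and the two windows.** Take the edge of the range in step 2, 20 new starters among users and 10 never-users among controls, with c = 1. From enrolment the contrast is d − (50/60)d = 0.17d; from day 14 it is (20/60)d − 0 = 0.33d. The windows agree in expectation but can differ in a given draw. With Aim 2 arm in the model as a main effect, the stratum contrasts (0 for former users, d for never-users) are weighted by 40×50/90 = 22.2 and 20×10/30 = 6.7, giving 6.7/28.9 × d = 0.23d from either window.

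**5. What each stratum can show.** Detectable d at 80% power: 0.60 for continuers vs those who return the watch (45 vs 45); 1.06 for new starters vs never-users (15 vs 15). For the Aim 2 arm × Aim 3 arm interaction it is about (1.96 + 0.84) × √(2/45 + 2/15) = 1.18.

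**6. The adherence clock.** Aim 3 day 1 is wear day 15 for about 45 users and wear day 1 for about 15. The two groups share only wear days 15 to 30. A single day slope averages first use with later use, about 15:45.

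**The case against.** The strongest reply is that the Aim 3 comparison is valid as it stands. Assignment at day 14 is random, so the Aim 2 arm is balanced in expectation and the contrast is an unbiased average effect of what is offered in days 15 to 44. That is right. A reader might infer confounding from the mixed history, and the documents do not support it.

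Several other stronger readings also go too far:

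- *That nothing in the plan uses the Aim 2 arm.* Protocol section 11 (Questionnaire) compares changes from baseline to day 14 between the 90 and the 30. That is a randomised user vs non-user comparison on overlapping outcomes, and read beside Aim 3 it helps to judge carry-over. The gap is confined to the Aim 3 models.
- *That the draw is unstratified.* The documents do not say how it is made, and the diagram is not shown. The supportable statement is that stratification is not stated.
- *That the contrast is simply continuing vs stopping for three quarters of participants.* Continuers also receive the AliveCor device, which section 11 introduces in Aim 3. The 0.25d figure assumes that this and 30 more days of wear add nothing.
- *That former Aim 2 controls are a true usual-care group.* They wore study ECG patches for 14 days, with abnormal findings passed to their physicians.

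The patient-reported comparison is secondary in both documents and exploratory in the objectives. The covariate lists are open, and characteristic-by-time interactions are already foreseen, so the Aim 2 arm fits the models. What stands against this is that a design variable should be named in advance, and the label should match the group.

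**Conclusion.** The point holds as one of analysis and labelling. In expectation three quarters of the Aim 3 controls are former Pulsewatch users (45 of 60; 40 to 50 under simple random selection), and a quarter of the users are new starters. The Aim 3 contrast estimates the average effect of being offered Pulsewatch plus AliveCor, rather than no study device, during days 15 to 44 in a mostly pre-exposed sample. It is not a contrast with usual care. Carry-over from Aim 2 would dilute it; under the assumptions shown, it lies between d and 0.25d.

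The adherence slope mixes two stretches of wear. This needs no carry-over assumption and bears on the primary Aim 3 analysis. The Aim 2 accuracy results are not affected. The change is cheap and worth making, but not a condition for proceeding. The SAP's 30 continuing users against the protocol's 60 mixed users is a separate matter of document alignment.

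**What to change.** 1. State that the day-14 Aim 3 randomisation is stratified by Aim 2 arm, if it is still open.
2. Add Aim 2 arm as a fixed effect in the patient-reported regression and in the adherence model, and Aim 2 arm × day in the adherence slope (Protocol section 13; SAP Table 2 and Aim 3 Analysis). Say that day counts from the start of Aim 3, and give the matching wear days for each group.
3. Report the Aim 3 contrast separately by Aim 2 arm, with confidence intervals and as description only.
4. In Protocol sections 4 and 13 and in the SAP Aim 3 Analysis, replace usual care with a plain description: no study device in days 15 to 44. Claim a usual-care contrast for neither stratum.
5. Reconcile the change-score window: day 14 to day 44 in section 11 against baseline to 1 month in section 13 and the SAP.

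The cost is one stratification factor already on file, one or two model terms and some wording. The one drawback is candour: the report will show that the comparison of starting with never using rests on about 15 vs 15 people.
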